5.5.3 Exclusion criteria

- For females: known pregnancy or breast feeding
- Participants who have received artemisinin or a derivative or an artemisinin-containing combination therapy (ACT) within the previous 7 days.
- History of allergy or known contraindication to artemisinins, lumefantrine or multivitamins
- Documented or claimed history of cardiac conduction problems
- Severe vomiting or diarrhoea
- Signs/symptoms of clinical malaria (febrile or history of fever in the previous 24 hours) confirmed by RDT.

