6.2.1. Demographics and Medical History

Basic demographic and epidemiological data (e.g. sex, age, weight, address, bed net use, malaria risk factors, travel history, prior malaria episodes, prior treatment and previous participation in this or previous studies), and a full medical history will be recorded by the study staff.

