6.6. Follow-up

Participants will be asked to return for a follow-up assessment any time from 28 to 35 days after commencing prophylaxis. This will be regardless of the duration of their visit to the forest or the number of times they visited it in that period. At this assessment, they will be interviewed about how long they spent in the forest, where they went, why, who they travelled with and about risk factors for infection. Brief physical examinations, vital sign and symptom questionnaire will be performed. They will also be asked to report any diagnostic tests and/or treatment for malaria during the preceding 28-35 days.

Blood sampling at follow-up

At each follow-up visit, the following blood will be taken:

All individuals:

- Parasite PCR (Up to 1 ml).

- Dried blood spot for lumefantrine level (0.2 ml)

In those with confirmed clinical malaria at any time point between enrolment and follow-up:

- Dry blood blots (0.4 ml, 3 spots) collected on filter papers for:
 - o Parasite DNA genotyping for genetic markers of antimalarial resistance.
 - o Parasite whole genome sequencing and barcoding to identify geographical origin of parasites and compare genotypes to identify persistent infections.

In individuals who are planning to return again to the forest within the following 28 days after the follow up visit, they will be asked to continue their weekly prophylaxis according to the original treatment allocation on enrolment. They will then be asked to return for a second follow-up visit a further 28 to 35 days later when the above procedure will be repeated. This will be repeated one more time. If the person cannot be followed up within the scheduled period, e.g. because they do not return from the forest in time, then they will be followed up at the first opportunity and this will be recorded in the CRF.

Thus individuals may take prophylaxis continuously for a maximum of 3 periods of 28-35 days in the forest plus 4 weeks after returning totaling 112 days. The choice of study medication for each individual will follow the initial assignment on enrolment throughout the follow-up period.

In those who do not declare an intention to return to the forest within 28 days at any follow-up visit, no further follow-up visits will be offered at that time but they will be asked to complete 4 weeks of prophylaxis following their last day in the forest as post-exposure prophylaxis.

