18 APPENDIX 1. SCHEDULE OF ASSESSMENTS

TEST/APPLICATION	SCREENING	D0	D1	D2	CCM*	D28-35	CCM*	D56-63	CCM*	D84-91	CCM* up to D112
Informed consent	X										
Demographics		X									
Risk history		X				X		X		X	
Travel history		X				X		X		X	
Medical and drug history		X									
Symptoms questionnaire		X				X		X		X	
Temperature		X									
Weight		X									
Randomisation and assign study ID		X									
AL/multivitamin doses to be given		X	X	X							
Plasmodium PCR		X				X		X		X	
Blood for storage (serology)		X									
Plasmodium genetic analysis (DBS)					X*		X*		X*		X*

*CCM = episode of confirmed clinical malaria between enrolment and follow-up

19 APPENDIX 2. DOSING SCHEDULES**19.1 Artemether-lumefantrine**

Artemether -lumefantrine dosing schedule										
One tablet AL contains 20 mg artemether and 120 mg lumefantrine (Coartem)										
	No. of tablets recommended at approximate timing of dosing									
	Day 1		Day 2		Day 3		Day 8		Weekly	
Weight: Kilogram	0h	8h	24h	36h	48h	60h	168h	176h	336h	344h
15 - <25	2	2	2	2	2	2	2	2	2	2
25 - <35	3	3	3	3	3	3	3	3	3	3
≥35	4	4	4	4	4	4	4	4	4	4
Alternative preparation: one tablet AL contains 80 mg artemether and 480 mg lumefantrine (Artefan)										
	No. of tablets recommended at approximate timing of dosing									
	Day 1		Day 2		Day 3		Day 8		Weekly	
Weight: Kilogram	0h	8h	24h	36h	48h	60h	168h	176h	336h	344h
≥35	1	1	1	1	1	1	1	1	1	1

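### No pregnancy question is listed at the follow-up visits, although study drug can continue after each one and section 6.13 acts only on a reported pregnancy

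*Protocol*

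**What the plan says.** **Entry.** Women aged 16 to 65 may enrol. Protocol section 5.5.3 excludes "For females: known pregnancy or breast feeding". No pregnancy test is listed. At enrolment, section 6.2.1 adds that "a full medical history will be recorded by the study staff".

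**Follow-up visits.** Section 6.6 lists an interview on forest trips and risk factors and blood samples. On the clinical side it says "Brief physical examinations, vital sign and symptom questionnaire will be performed". The only other history it asks for is on malaria: "They will also be asked to report any diagnostic tests and/or treatment for malaria during the preceding 28-35 days". In Appendix 1 the row "Medical and drug history" is marked at D0 only, and no row mentions pregnancy at any visit.

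**Dosing after a visit.** For those planning to go back to the forest within 28 days, "they will be asked to continue their weekly prophylaxis according to the original treatment allocation on enrolment". For the others, "they will be asked to complete 4 weeks of prophylaxis following their last day in the forest as post-exposure prophylaxis". The stated ceiling on continuous use is "a maximum of 3 periods of 28-35 days in the forest plus 4 weeks after returning totaling 112 days".

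**Pregnancy during the study.** Section 6.13 requires immediate withdrawal when a pregnancy is reported to the team, notice to the principal investigator within one working day, and efforts to learn the outcome, recorded on a pregnancy form.

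**Re-enrolment.** Someone who joins again for a new episode is re-randomised by the enrolment procedure (6.6), and 6.3 admits to randomisation only those who meet no exclusion criterion.

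**The concern.** The protocol treats pregnancy as a reason not to start study drug and as a reason to leave the study at once. Between those two points it lists nothing that would bring a pregnancy to light. A participant may take drug for up to 112 days under one enrolment. At each visit the decision on further dosing turns, as written, on forest plans alone. A woman who becomes pregnant, or learns that she is, after D0 is withdrawn only if she raises it herself.

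The treatment of re-enrolment sharpens the point. A participant starting a new episode passes the exclusion criteria again, while one who continues through three periods has no listed re-check. What is at stake is avoidable exposure to AL in pregnancy. The sample size, the power and the primary analysis do not depend on it.

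**Working it through.** **1. Do the listed visit items prompt a report of pregnancy?**

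| Item at D28-35, D56-63, D84-91 | Source | Asks about pregnancy? |
|---|---|---|
| Forest, travel and risk interview | 6.6, Appendix 1 | No |
| Brief examination, vital sign | 6.6 | No |
| Symptom questionnaire | 6.6, section 8, Appendix 1 | Not stated; contents not available |
| Malaria tests and treatment | 6.6 | No |
| PCR and lumefantrine samples | 6.6 | No |

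The symptoms tabulated in SAP Tables 1 and 6a include nausea, vomiting and fatigue but no pregnancy item. This is only indirect evidence of what the questionnaire contains.

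**2. How much dosing could a positive answer avert?**

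Inputs: three periods, taken at 28 days each, and 4 weeks (28 days) after return (6.6); AL given on one day per week, 2 doses on that day (6.5).

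The protocol's own figure: 3 × 28 + 28 = 112 days. It reproduces.

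Doses averted = (112 − visit day) / 7 × 2.

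| Visit | Days left | Weekly dosing days | AL doses |
|---|---|---|---|
| Day 28 | 112 − 28 = 84 | 84 / 7 = 12 | 12 × 2 = 24 |
| Day 56 | 112 − 56 = 56 | 56 / 7 = 8 | 8 × 2 = 16 |
| Day 84 | 112 − 84 = 28 | 28 / 7 = 4 | 4 × 2 = 8 |

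A participant with no plan to return, whose last forest day falls at the visit, has 28 post-exposure days left: 28 / 7 = 4 dosing days, or 8 doses. An earlier last forest day leaves fewer.

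These are ceilings for the AL arm, since they assume that the participant would otherwise use the full 112 days. With every period at the 35-day end of the visit window, total use would be 3 × 35 + 28 = 133 days, but the protocol states 112 and the table keeps to that.

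**3. What would withdrawal cost the comparison?**

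SAP section 2.2 counts the primary endpoint at the Month 1, 2 and 3 follow-ups. If the visit's own sample is taken first, withdrawal at D28-35 loses up to two later PCR visits, at D56-63 up to one, and at D84-91 none under that enrolment. Data up to withdrawal are kept (6.13).

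**The case against.** The strongest reply is that silence proves little here. Appendix 1 is plainly incomplete. It has no row for eligibility even at D0, none for physical examination or lumefantrine level, and it marks study drug on the first three days only. A pregnancy form exists, and the CRF, questionnaire and consent pages may carry the prompt. This stands as a limit on the point. It does not answer it, because the text of 6.6 sets out the visit in some detail and has the same gap.

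A second reply points to other routes. Participants are urged to tell the team of unexpected symptoms or illness (section 8) and of visits to health workers (6.6.2), other medication is recorded (7.4), and the investigator may stop anyone (6.13). None of these prompts a report of pregnancy, which a participant may not regard as a symptom or an illness. Investigator discretion works only once the investigator knows.

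Third, the protocol is consistent with itself: known pregnancy at entry, withdrawal on report. That is fair. The point is a cheap safety improvement to a design choice, and no contradiction is alleged.

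A reader might go further and infer that every exclusion in 5.5.3 should be re-checked as a matter of safety. The documents do not support giving the others equal weight. The examination, the questionnaire and the stopping provisions in 6.13 largely cover a symptomatic allergy or cardiac problem, and 12.4.1 states that AL is not known to prolong the QTc interval harmfully. Breast feeding that begins by day 84 would ordinarily mean a late pregnancy already present at entry, which 5.5.3 excludes if known.

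**Conclusion.** The point holds for pregnancy. As listed, the three follow-up visits include no question about it, further dosing does not depend on it, and the withdrawal rule waits for a report that nothing prompts. In the AL arm, a pregnancy disclosed at day 28, 56 or 84 would avert at most 24, 16 or 8 AL doses on the stated 112-day maximum. The documents give neither the number of women affected nor a figure for the risk of AL in pregnancy, so the expected benefit cannot be sized.

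Two further inferences should be resisted. One is that the change leaves the arm comparison untouched: withdrawal under 6.13 removes later outcomes, so the effect is probably small rather than nil. The other is that the gap threatens the trial's validity: nothing in the endpoints, randomisation or sample size rests on it.

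The conclusion assumes that the unseen CRF and questionnaire do not already ask. If they do, only the wording of 6.6 and Appendix 1 is at issue.

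**What to change.** Add to section 6.6, with one matching row in Appendix 1 at D28-35, D56-63 and D84-91:

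> Before any further study drug, including post-exposure doses, female participants are asked about known or suspected pregnancy; the answer is recorded in the CRF and a reported pregnancy is handled under 6.13.

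If the CRF or questionnaire already contains the question, state that in both places instead. Asking again about breast feeding, allergy and cardiac conduction at the same moment is optional.

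The cost is one short question at visits already held and one schedule row, with no test and no extra visit. There are two downsides. A verbal question misses early pregnancy that the woman has not recognised, and the few participants withdrawn contribute no later follow-up outcomes. The visit's PCR sample should be taken before withdrawal so that the current month's outcome is kept.

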6.6.1 Time windows

The time-window for the follow-up visits is 28-35 days. If a participant does not attend, the study team will try to locate the participant and bring them to the village.

6.6.2 Additional visits

Participants presenting to the village malaria worker, mobile malaria worker or clinic with a fever or other symptoms at any time after enrolment that is not a scheduled study follow-up visit will be assessed and treated by the healthcare workers in the local healthcare system as per routine clinical practice in Cambodia.

On enrolment, participants will be encouraged to attend a village malaria worker or government clinic for the assessment of fever or other symptoms and to report this to the study team as soon as possible after the symptoms occur. Information on these healthcare encounters including malaria test result and treatment will be recorded in the study CRF.

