3.3 Proposed activities

Artemether-lumefantrine prophylaxis trial

The study of AL versus a multivitamin will be a two-arm randomised open label comparative study. Laboratory assessments of malaria infection at baseline and day 28 post forest will be performed blind to treatment allocation and incidence of clinical cases during follow-up will be recorded.

Activities/outcomes

The main activity proposed is an *in vivo* clinical assessment of prophylaxis to prevent malaria in 4400 participant episodes in 50 villages in Stung Treng and Pursat Provinces, Cambodia. The subjects will be randomized in a one-to-one ratio between the ACT AL and a multivitamin preparation with no antimalarial activity.

The study sites have been chosen based on current information on incidence of malaria, known predominance of malaria among forest goers, presence of an established clinical research programme and feasibility to perform the proposed research activities.

Efficacy of AL ACT will be assessed through follow up visits 28 days (+/-7 days) after returning from the forest upon completing each course of prophylaxis when temperature, symptom questionnaires, brief physical examinations, and malaria parasite PCR, and, in selected individuals, parasite genetics will be performed. Episodes of confirmed clinical malaria among study participants at any time point between enrolment and follow-up will also be recorded.

All the organisations in this collaboration will work closely with local counterparts including the National Malaria Control Programmes (NMCPs), non-governmental and other relevant organisations. Training is an integral part of this collaborative working relationship, and the building of local research capacity is an essential component of all research plans.

All research-related activities, from study design, planning, implementation through to analysis and writing of reports will be performed jointly with local counterparts. Both on-the-job training and formal training will be provided when needed, in particular for Good Clinical Practice (GCP) skills.

The close interaction between WHO and its regional offices will ensure that new knowledge is disseminated efficiently and effectively throughout the region.

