5.4 Primary and secondary endpoints

5.4.1. Co-primary Endpoints

1. 28-day PCR positivity rate of *Plasmodium* infections of any species.
2. Proportion of participants with confirmed clinical malaria of any species reported between day 0 and day 28

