6.3. Randomisation and blinding

Participants who fulfil all the inclusion criteria and have none of the exclusion criteria will be randomised 1:1 to one of the two treatment arms according to a randomisation schedule. Randomisation will be in blocks of size that will be determined by the trial statistician and the block

size will not be revealed to the investigating team. Allocation will be done by drawing the next sequential numbered opaque envelope (or other equally reliable randomisation administration procedure), which contains the study number and treatment allocation.

The participants will be assigned a study arm through a computer-generated randomisation schedule. Individual, sealed and sequentially numbered envelopes will be provided for each trial site with one envelope per participant, indicating the treatment allocation.

This is an open-label study so the blinding of investigators and participants is not applicable. However, the randomisation procedure allows for adequate drug allocation concealment before envelopes are opened. All laboratory investigations will be performed without knowledge of the treatment allocation.

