# 4.4.6 Prevalence of asymptomatic Plasmodium infections in high risk populations at varying seasonal time points

Prevalence of asymptomatic Plasmodium at baseline, stratified by season and risk factors will be presented in table 7 below. The numbers of asymptomatic Plasmodium infections will be visuallized by follow-up months and study arm in figure 2 below.

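### Confirmed clinical malaria is found only through care that unblinded participants sought, and the SAP reports it only merged with blind-read PCR, so the two cannot be told apart

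*Protocol*

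**What the plan says.** **Endpoints.** Protocol 5.4.1 lists two co-primary endpoints. One is 28-day PCR positivity for any species. The other is "Proportion of participants with confirmed clinical malaria of any species reported between day 0 and day 28". SAP 2.2 and 4.3 join them with an *or* and call the result a composite. SAP Table 2, and Table 3 by species, have one rate per arm and one effect estimate per row. Neither table shows the two parts separately.

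**Blinding.** Protocol 6.3: "This is an open-label study so the blinding of investigators and participants is not applicable". Only the laboratory works without knowledge of allocation.

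**Detection of clinical malaria after enrolment.**
- Protocol 6.6.2 has local health workers assess participants who present "with a fever or other symptoms at any time after enrolment that is not a scheduled study follow-up visit". Participants are encouraged to attend and to tell the study team, and test results are entered on the CRF.
- Protocol 6.6, at the follow-up visit: "They will also be asked to report any diagnostic tests and/or treatment for malaria during the preceding 28-35 days".
- Protocol 6.11 links participants with a confirmed episode to their case records.

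**Entry compared with follow-up.** Protocol 5.5.3 excludes people with "Signs/symptoms of clinical malaria (febrile or history of fever in the previous 24 hours) confirmed by RDT". For follow-up, 3.3 describes visits "when temperature, symptom questionnaires, brief physical examinations, and malaria parasite PCR" will be done, and 6.6 lists examination, vital sign and symptom questionnaire. Neither mentions a rapid test. Appendix 1 marks the row "Symptoms questionnaire" at day 0 and every follow-up visit, but marks temperature at day 0 only.

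**Asymptomatic infection.** SAP 4.4.6: "The numbers of asymptomatic Plasmodium infections will be visuallized by follow-up months and study arm". It does not say how an infection found at follow-up is classed as asymptomatic.

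**The concern.** The two co-primary endpoints are measured with unequal protection against bias. PCR is taken from every attender at a fixed visit and read blind. Clinical malaria needs a participant who knows the arm to feel ill, decide to seek a test and get one. If that behaviour differs between people who know they take an antimalarial and people who know they take a vitamin, the clinical endpoint differs between arms with no drug effect.

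Open-label detection is a design choice, and the analysis can make its influence visible. The SAP does the opposite. It folds the exposed component into the protected one, shows no breakdown, and tabulates no malaria tests by arm. A reader of the final tables could not tell whether a difference came from PCR or from testing behaviour. The Protocol's second co-primary endpoint would not be reported as such at all.

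**Working it through.** **Step 1: does any route avoid care-seeking?**

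| Route | Place | What it needs |
|---|---|---|
| Attendance at a village malaria worker or clinic | Protocol 6.6.2 | Participant decides to attend |
| Recall at the follow-up visit | Protocol 6.6 | A test or treatment already received |
| Linkage to case records | Protocol 6.11 | A record, hence a test already done |

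Protocol 8 also encourages participants to report illness between visits, but a reported symptom is not a confirmed case. Protocol 6.8.1 has PCR-positive participants followed up, but results come 3 to 6 months after sampling. That is too late for a day 0 to 28 endpoint, and nothing says such cases are reclassified. As written, every route depends on care sought.

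**Step 2: what does PCR cover?** Every attender gives a PCR sample at the scheduled visit (Protocol 6.6, 6.12.1). A febrile, parasitaemic attender should count as PCR-positive and so enters the composite. The cover is incomplete in one respect: an episode treated before the visit may be PCR-negative by then.

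**Step 3: the plan's own figure.** Protocol 9.1 and SAP 2.5 give 1,605 episodes per arm for 5% against 3%, 80% power, 5% significance. The two-sided two-proportion formula with continuity correction returns 1,605 exactly. That figure concerns *P. falciparum* PCR positivity. Neither document gives an expected clinical malaria rate or a care-seeking proportion, so what follows is illustration.

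**Step 4: size under assumptions.** All of these are assumed: no drug effect; test-seeking of 70% on multivitamin and 60% or 50% on AL; detected clinical malaria of 1% or 2% on multivitamin; 5% PCR positivity in both arms (borrowed from the Pf sizing rate); no overlap between components, which maximises the effect on the composite; 2,200 episodes per arm; no clustering or losses.

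Clinical ratio = AL test-seeking / multivitamin test-seeking:
- 0.60/0.70 = 0.86
- 0.50/0.70 = 0.71

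Composite ratio = (PCR + clinical on AL) / (PCR + clinical on multivitamin):
- mildest case: (5 + 1 × 0.86)/(5 + 1) = 5.86/6 = 0.98
- strongest case: (5 + 2 × 0.714)/(5 + 2) = 6.43/7 = 0.92

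Chance of a significant result favouring AL = Φ(d/SE − 1.96), where d is the risk difference and SE = √[(p₁(1−p₁) + p₂(1−p₂))/2,200]. The nominal value in that direction is 2.5%.

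| Endpoint | Multivitamin v AL | d/SE | Chance |
|---|---|---|---|
| Clinical alone, mildest | 1.00% v 0.857% | 0.00143/0.00289 = 0.49 | 7% |
| Clinical alone, strongest | 2.00% v 1.429% | 0.00571/0.00391 = 1.46 | 31% |
| Composite, mildest | 6.00% v 5.857% | 0.00143/0.00712 = 0.20 | 4% |
| Composite, strongest | 7.00% v 6.429% | 0.00571/0.00755 = 0.76 | 11% |

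If people on AL seek tests more, the ratios invert: 1/0.86 = 1.17 and 1/0.714 = 1.40 for the clinical endpoint, and 6/5.86 = 1.02 and 7/6.43 = 1.09 for the composite. The bias then works against AL.

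**The case against.** **The composite dilutes the bias.** On the assumptions above the composite ratio stays between 0.92 and 0.98. This stands. But the dilution depends on how much of the composite is clinical, which the SAP does not show, and the Protocol names clinical malaria as a co-primary endpoint in its own right.

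**The direction is unknown.** People on a vitamin may test more because they know they are unprotected. Equally, Protocol 12.4.1 lists headache, dizziness and asthenia among the commonest adverse events with AL, and these could prompt more testing on AL. This stands, and is the reason to report tests by arm rather than presume a direction.

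**There are safeguards.** Record linkage does not depend on reporting to the study, and SAP Table 5 shows other antimalarial use by arm. Both help. Linkage still needs a test, and Table 5 does not give tests or their results.

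**A reader might infer that the trial loses malaria present on the visit day.** The documents do not support this for the composite, because PCR is taken at that visit. Only the separate clinical component and the symptomatic or asymptomatic label are affected. Nor is there sign of bias between arms in that gap: if a fixed share of PCR-positives is febrile, the cases missed follow the infection ratio itself. Visits also run from day 28 to 35, so some fall outside the day 0 to 28 window.

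**A reader might infer from 6.6.2 that febrile attenders at scheduled visits go untested.** That section defines an additional visit, and the Protocol is otherwise silent. Appendix 1 also lacks rows for lumefantrine sampling and physical examination, which 6.6 requires, so the schedule is simply incomplete.

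**A reader might infer that SAP Figure 2 would plot febrile cases as asymptomatic.** The figure is not shown, and 4.4.6 gives no rule either way. Symptom data exist at every follow-up visit.

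**Conclusion.** The point holds as a reporting weakness in the analysis plan. From the text alone, clinical malaria after enrolment is found only through care sought by unblinded participants, and the SAP merges it with blind-read PCR without a split or a count of tests.

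The size cannot be derived from the documents. On the assumed inputs, differential test-seeking alone gives a clinical ratio of 0.86 to 0.71 and a composite ratio of 0.98 to 0.92, or the reciprocals if behaviour runs the other way. The blind-read PCR endpoint is not threatened by testing behaviour as such, although cases treated before the visit can drop out of it.

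The documents do not show that a bias exists, that it favours AL, or that visit-day infections are lost from the primary composite. They show that, if a bias arose, the planned tables would hide it.

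**What to change.** 1. **SAP 4.3.2 and Table 2, and Table 3 by species:** report the 28-day PCR endpoint and the clinical malaria endpoint separately beside the composite, using the same model and the same handling of repeat episodes.
2. **SAP 4.3.2, new table:** by arm and follow-up period, give the number of malaria tests sought and the share positive, from the CRF data under Protocol 6.6 and 6.6.2.
3. **SAP 4.4.6:** count a follow-up infection as asymptomatic only if the symptom questionnaire and vital signs show no fever and there is no confirmed clinical malaria.
4. **Protocol:** reconcile Appendix 1, which marks temperature at day 0 only, with 3.3 and 6.6, which list temperature or vital signs at follow-up. Whether febrile attenders are tested at scheduled visits is for the investigators to state.

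The cost is wording plus some extra table rows. Items 1 and 2 need no new data. Item 3 uses the symptom questionnaire and the vital signs that Protocol 6.6 already requires. Item 4 brings two parts of the Protocol into line. The separate clinical estimate will be less precise than the composite, since no sample size was set for it, and should be presented with that caveat.
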